2.5.2 Data handling conventions for secondary efficacy variables

Fasting condition

FPG measurement not collecting in fasting condition will not be used in the analyses.

Invalid laboratory data

HbA1c or FPG measurements flagged as invalid by the laboratory will not be used in the analyses.

HbA1c target

HbA1c target missing data handling

• Patients with missing HbA1c data at respectively Week 12 and Week 24 will be regarded as not having reached the HbA1c target (ie, as failure) at each given time-point.

Composite endpoints missing data handling

- For each cases presented above regarding missing HbA1c values the patient will be considered as failure for each composite endpoint of the corresponding randomized period,
- For each case presented above regarding missing hypoglycemia event information the patient will be regarded as failure for each related composite endpoint,
- In case of premature end of study during the 24 weeks randomized period the patient will be considered as failure for each composite endpoint relative to the 24 weeks period.

Change in HbA1c category

Patients with missing:

- Baseline HbA1c will be regarded as not having reached the HbA1c target at Week 12 and Week 24,
- HbA1c data at respectively at Week 12 and Week 24 will be regarded as not having reached the HbA1c target at each given time-point.

HABS

The Hypoglycemic Attitudes and Behavior Scale consists of 14 items within 3 domains measuring anxiety (5 items), confidence (5 items) and avoidance (4 items) related to hypoglycemia. The 3 domain scores are determined by computing the mean of item responses. At least 2/3 of the items should be completed for the calculation of each domain score, which means only one item missing is acceptable to calculate each domain score. If more than one item is missing, the domain score is considered as missing.

DTSQc and DTSQs

The total treatment satisfaction score is the sum of items 1, 4, 5, 6, 7 and 8.

If no more than 2 out of the 6 questions comprising the total treatment satisfaction score are missing, the total treatment satisfaction score is imputed by calculating the average of the scores from the answered questions, dividing this sum by the number of answered questions and multiplying the average by six.

If items 2 or 3 are not answered, frequency of hypoglycemia or hyperglycemia scores is considered as missing.

• In- between scores

If a patient answers in-between response choices (eg, between 1 and 2), the score will be coded as 1.5.

- If a question is answered twice
 - If the scores that have been circled are next to each other (ie, 2 & 3), then the mid-point between them will be taken (ie, 2.5) as this is unlikely to be a mistake and more likely to represent difficulty in choosing a score.
 - However, if the two answers are not immediately next to each other (ie, 2 and 5 on the DTSQ, or 3 and 0 on the DTSQc), answers will be considered as missing.

Scoring issues	DTSQs	DTSQc							
In between score	If patients answer in betweer (i.e	n choices, score should be coded as mean of both scores .: if between 2 and 3 coded 2.5)							
Item answered twice using 2 consecutive scores	۸ (ie,: if 1 an	Midpoint score should be used (ie,: if 1 and 2 are answered should be coded 1.5)							
Item answered twice but using non-consecutive scores		Score is set to missing							
Item is circled but accompanied by word	Onlys	score should be taken into account							
If respondent as circle word of the extremes of the scale instead of value	Score should be the nearest value (ie,: 0 or 6)	Score should be the nearest value (ie,: -3 or 3)							

Table 2 – Unexpected Scoring

Statistical Analysis Plan HOE901 - LPS14584 -insulin glargine U300 03-Jul-2017 Version number: 1

PRO scales	Score	Number of items included in score derivation	Minimum number of items required for score calculation
HABS	Anxiety score	5	4
	Confidence score	5	4
	Avoidance score	4	3
DTSQs	Total treatment satisfaction score	6	4
	Perceived frequency of hyperglycemia score	1	1
	Perceived frequency of hypoglycemia score	1	1
DTSQc	Total treatment satisfaction score	6	4
	Perceived frequency of hyperglycemia score	1	1
	Perceived frequency of hypoglycemia score	1	1

Table 3 – PRO Missing Data Handling

Effect Size

The effect size is defined as: ES= difference/SD where SD is the standard deviation. Note that there are two main types of effect size:

- Within ES: Calculated at the group level, when focusing on change from baseline
- Between ES: Calculated when comparing treatments groups

The within-group ES (WES) indicates if the changes from baseline to the end of treatment are clinically meaningful for each group.

$WES = \frac{LS mean \ change \ from \ baseline \ at \ timepoint \ t}{pooled \ baseline \ standard \ deviation}$

The between-group ES (BES) indicates if the mean changes from baseline to the end of treatment are clinically meaningful between groups.

 $BES = \frac{difference in LS means between groups at timepoint t}{pooled baseline standard deviation}$

Cohen's rules for Effect Size (ES) and interpretation ES >0.2: Negligeable $0.2 \le ES < 0.5$: Small $0.5 \le ES < 0.8$: Moderate ES ≥ 0.8 : Important

Handling of missing data in the calculation of the percentage of patients reaching a prespecified HbA1c value

Patients without any available assessment at week 12 or week 24 will be considered as failures (non-responders) in the analysis.

Handling of missing data in the calculation of average pre-breakfast SMPG

At least 3 pre-breakfast SMPG values in the last 7 days are required to be taken into account in the statistical analyses (including descriptive analyses at each time-point).

Only fasting SMPG will be analysed.

Handling of missing data in the calculation of SMPG variables (4 points and 8 points profiles)

At least 5 measurements from the 8 points profile are required for analyzing the profile by time-point, the 24-hour mean SMPG and the corresponding variability.

At least 3 measurements from the 4 points profile are required for analyzing the profile by time-point.

Handling of missing data in the calculation of daily basal insulin dose

At each visit, the average daily basal insulin doses will be calculated as the average of the daily basal insulin doses available in the week before the visit. No minimum number of available doses will be required.

If the body weight measurement is missing at a given visit, the last available measurement from previous visit is used

In case of any missed doses, corresponding days should not be taken into account in the determination of the average daily insulin doses. In case of premature discontinuation or use of rescue medication, the average daily dose taken into consideration for a patient is the one measured the week before such event.

2.5.3 Missing data

For categorical variables, patients with missing data are not included in calculations of percentages unless otherwise specified. When relevant, the number of patients with missing data is presented.

Handling of computation of treatment duration if investigational medicinal product end of treatment date is missing

For the calculation of the treatment duration, the date of the last dose of IMP is equal to the date of last administration reported on the end-of-treatment case report form page. If this date is missing, the exposure duration should be left as missing.

The last dose intake should be clearly identified in the case report form and should not be approximated by the last returned package date.

Handling of medication missing/partial dates

No imputation of medication start/end dates or times will be performed. If a medication date or time is missing or partially missing and it cannot be determined whether it was taken prior or concomitantly, it will be considered a prior, concomitant, and post-treatment medication.

Handling of adverse events/hypoglycemia with missing or partial date/time of onset

Missing or partial adverse event onset dates and times will be imputed so that if the partial adverse event onset date/time information does not indicate that the adverse event started prior to treatment or after the treatment-emergent adverse event period, the adverse event will be classified as treatment-emergent. No imputation of adverse event end dates/times will be performed. These data imputations are for categorization purpose only and will not be used in listings. No imputation is planned for date/time of adverse event resolution.

Handling of adverse events/hypoglycemia when date and time of first investigational medicinal product administration is missing

When the date and time of the first IMP administration is missing, all adverse events that occurred on or after the day of randomization should be considered as treatment-emergent adverse events. The exposure duration should be kept as missing.

The last dose intake should be clearly identified in the case report form and should not be approximated by the last returned package date.

Handling of missing assessment of relationship of adverse events to investigational medicinal product

If the assessment of the relationship to IMP is missing, then the relationship to IMP has to be assumed and the adverse event considered as such in the frequency tables of possibly related adverse events, but no imputation should be done at the data level.

Handling of potentially clinically significant abnormalities

If a patient has a missing baseline he will be grouped in the category "normal/missing at baseline."

For PCSAs with 2 conditions, one based on a change from baseline value or a normal range and the other on a threshold value, with the first condition being missing, the PCSA will be based only on the second condition.

For a PCSA defined on a threshold and/or a normal range, this PCSA will be derived using this threshold if the normal range is missing.

Measurements flagged as invalid by the laboratory will not be summarized or taken into account in the computation of PCSA values.

Handling hypoglycemia with missing or partial time

No imputation for missing or partial time of hypoglycemia will be done.

However:

- if the minutes are missing and the hours comprised between 00 and 05, the event will be considered as nocturnal,
- if hours are missing and the patient was awaken during nocturnal, the event will be considered as nocturnal (defined by clock time).

Handling of hypoglycemia event classification when some classification items are missing

In case of information missing on the item 'Assistance required', the following algorithm was applied:

In case of 'assistance required' equal to 'No' and information missing on one of the items 'Associated with clinical symptoms', 'Plasma glucose' or 'Countermeasures', the following algorithm was applied:

As a conclusion, for cases where hypoglycemia could not be fully classified, as described above, two categories will therefore be created:

- hypoglycemia classified as 'Non classified Hypoglycemia (severity unknown) if the variable 'assistance required' is equal to 'missing'
- hypoglycemia classified as Non classified Hypoglycemia (non-severe) if the variable 'assistance required' is equal to 'No'.

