2.1.4 Safety endpoints

The safety analysis will be based on:

- All hypoglycemia events (according to American Diabetes Association [ADA] Workgroup on Hypoglycemia),
- Local tolerability at injection site,
- Hypersensitivity reactions,
- Adverse events with special interest (AESI) with immediate notification:
 - Increase in alanine aminotransferases (ALT);
 - Pregnancy;
 - Symptomatic overdose with IMP/NIMP;
- Other adverse events (AE) or serious adverse events (SAEs),
- Vital signs including body weight.

In case of premature permanent IMP discontinuation or rescue therapy intake, the process described in Section 2.5.4 will be applied to retrieve safety assessments performed at the end of treatment visit or at pre-rescue visit.

Observation period for safety endpoints

The observation period of safety data will be divided into 3 segments:

• **The pre-treatment period** is defined as the time between the date of the signed informed consent and the first injection of open-label IMP.

- The on-treatment period (24-week on-treatment period / 24-week TEAE period) is defined as the time from the first injection of open-label IMP up to 7 days (or 2 days for hypoglycemia) after the last injection of open-label IMP, regardless of the introduction of rescue therapy. The 7-day interval is chosen based on the half-life of the IMP (approximately 5 times the half-life of Tresiba).
 - **12-week on-treatment period (12-week TEAE period)** is defined as the time from the first injection of IMP up to Week 12 or 7 days (or 2 days for hypoglycemia) after the last injection of IMP whichever comes earlier.
- **The post-treatment period** is defined as the time starting 8 days (or 3 days for hypoglycemia) after the last injection of open-label IMP (after on-treatment period). The baseline value for safety endpoints will be the last available value prior to the first injection of open-label IMP.

The on-study observation period is defined as the time from start of treatment until the end of the study (defined as last protocol planned visit or the resolution/stabilization of all serious adverse events and adverse events with pre-specified monitoring).

The baseline value for safety endpoints will be the last available value prior to the first injection of open-label IMP.

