2.4.3.2 Extent of investigational medicinal product exposure

The extent of IMP exposure will be assessed by the duration of IMP exposure.

Duration of IMP exposure is defined as last dose date – first dose date + 1 day, regardless of unplanned intermittent discontinuations (see Section 2.5.3 for calculation in case of missing or incomplete data). Duration of IMP exposure will be summarized descriptively as a quantitative variable (number, mean, SD, median, minimum, and maximum).

In addition, duration of treatment exposure will also be summarized categorically by numbers and percentages for each of the following categories and cumulatively according to these categories: up to 4 weeks, >4 to 8 weeks; >8 to 12 weeks; >12 to 16 weeks; >16 to 20 weeks; >20 to 22 weeks; >22 to 23 weeks; >23 to 24 weeks and > 24 weeks.

Additionally, the cumulative duration of treatment exposure will be provided, defined as the sum of the duration of treatment exposure for all patients, and will be expressed in patient years.

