2.4.5.2 Analyses of adverse events

Generalities

The primary focus of adverse event reporting will be on treatment-emergent adverse events. Pretreatment and post-treatment adverse events will be described separately.

If an adverse event date/time of onset (occurrence, worsening, or becoming serious) is incomplete, an imputation algorithm will be used to classify the adverse event as pretreatment, treatmentemergent, or post-treatment. The algorithm for imputing date/time of onset will be conservative and will classify an adverse event as treatment emergent unless there is definitive information to determine it is pretreatment or post-treatment. Details on classification of adverse events with missing or partial onset dates are provided in Section 2.5.3.

Adverse event incidence tables will present by SOC, HLGT, HLT, and PT, sorted in alphabetical order for each treatment group, the number (n) and percentage (%) of patients experiencing an adverse event. Multiple occurrences of the same event in the same patient will be counted only once in the tables within a treatment phase. The denominator for computation of percentages is the safety population within each treatment group.

Sorting within tables ensures the same presentation for the set of all adverse events within the observation period (pretreatment, treatment-emergent, and post-treatment). For that purpose, the table of all treatment-emergent adverse events presented by SOC and PT sorted by the internationally agreed SOC order and decreasing frequency of PTs within SOCs will define the

presentation order for all other tables unless otherwise specified. Sorting will be based on results for the Toujeo® treatment arm.

Analysis of all treatment-emergent adverse events

The following treatment-emergent adverse event summaries will be generated for the safety population.

- Overview of treatment-emergent adverse events, summarizing number (%) of patients with any,
 - Treatment-emergent adverse event;
 - Serious treatment-emergent adverse event;
 - Treatment-emergent adverse event leading to death;
 - Treatment-emergent adverse event leading to permanent treatment discontinuation.
- All treatment-emergent adverse event by primary SOC, HLGT, HLT, and PT, showing number (%) of patients with at least 1 treatment-emergent adverse event sorted by the SOC internationally agreed order. The other levels (HLGT, HLT, PT) will be presented in alphabetical order,

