2.5 DATA HANDLING CONVENTIONS

2.5.1 General conventions

The following formulas will be used for computation of parameters.

Reference day

The reference day for the calculation of extent of exposure, time to onset and relative days is the day of the first administration of IMP, denoted as Day 1.

Demographic formulas

Body Mass Index $(kg/m^2) = (Weight in kg)/(Height in meters)^2$.

Disease characteristics formulas

Duration of diabetes (years) = (Date of informed consent – date of diagnosis of diabetes +1)/365.25.

Age at onset of diabetes (years) = (Date of diagnosis of diabetes – date of birth +1) /365.25.

Duration of previous non-insulin anti-hyperglycemic treatment (years) = (Date of informed consent - date of first dose of previous non-insulin anti-hyperglycemic treatment +1) /365.25.

HbA1c transformation

To transform HbA1c in % to mmol/mol, the following formula is used:

IFCC = (10.93 * NGSP) - 23.50

NGSP (National Glycohemoglobin Standardization Program network) corresponds to HbA1c (%) and IFCC (International Federation of Clinical Chemistry network) to HbA1c (mmol/mol)

FPG and SMPG conversion From mg/dL to mmol/L: x 0.0555 From mmol/L to mg/dL: x 18.0148

Renal function formulas

No derivation because gender is not reported on e-CRF, so only central lab has this information.

Rate of hypoglycemia event per patient-year

Computed as [sum of number of episodes of hypoglycemia for all patients] / [sum of patient-year of exposure for all patients] with patient-year of exposure calculated per patient as number of days of exposure divided by 365.25.

Rate of hypoglycemia event per patient-year per study period:

- For ≤12 weeks: [sum of the number of episodes of hypoglycemia for all patients during the first 12 weeks] / [sum of patient-year of exposure for all patients during ≤12 weeks], with the patient-year of exposure during ≤12 weeks calculated as the number of days exposed during ≤12 weeks divided by (12x7),
- For >12 weeks to ≤24 weeks: [sum of the number of episodes of hypoglycemia since week 12 until week 24] / [sum of patient-year of exposure for all patients since week 12 until week 24], with the patient-year of exposure since week 12 until week 24 calculated as the number of days exposed since week 12 until week 24 (included) divided by (12x7),

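### The 24-week hypoglycemia rate counts events for two days after the last dose without the matching time, and a missing dose date blanks exposure with no rule that aligns the events

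*SAP*

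**What the plan says.** **Rate.** SAP 2.5.1 sets the crude rate as "sum of number of episodes of hypoglycemia for all patients] / [sum of patient-year of exposure for all patients". Each patient's share of the denominator is that patient's days on drug, converted to years by 365.25.

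**Time.** The SAP defines exposure once, in 2.4.3.2: "Duration of IMP exposure is defined as last dose date – first dose date + 1 day". No post-dose days are included.

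**Events.** SAP 2.4.5.1 analyzes events in the safety population over the on-treatment period of 2.1.4, which runs "up to 7 days (or 2 days for hypoglycemia) after the last injection of open-label IMP". The 12-week period in the same section ends at Week 12, or at the same post-dose limit if that comes first.

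**Missing dates.** For a last-dose date missing from the end-of-treatment page, SAP 2.5.3 states: "If this date is missing, the exposure duration should be left as missing". It also forbids using the date of the last returned package as a substitute. For a missing first-dose date, under a heading that names hypoglycemia, it states that "all adverse events that occurred on or after the day of randomization should be considered as treatment-emergent adverse events" and that exposure stays missing.

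**Model.** SAP 2.4.5.1 estimates rate ratios with an over-dispersed Poisson regression adjusted for the two randomization strata. It names no exposure offset.

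**The concern.** A rate per patient-year is interpretable only if every day on which an event could be counted is also a day in the denominator, for the same patients. The plan departs from this in two ways.

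First, every treated patient has two event-eligible days after the last injection that the exposure definition leaves out. This needs no missing data.

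Second, a missing dose date removes the patient's days. For a missing first-dose date the SAP says outright that the events still count. For a missing last-dose date it is silent: the numerator covers all patients and no rule takes these events out, but the end of the event window is then undefined.

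The protocol's introduction singles out hypoglycemia as a comparison of particular interest, and the SAP reports these rates by category and by period. Crude rates could be slightly too high. They could also rest on different patients from the modeled rate ratio, if the model drops patients without exposure.

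**Working it through.** The documents state no hypoglycemia rate, so there is no plan figure to reproduce for this point. The one design figure, 460 patients per arm for HbA1c, is unaffected. It reproduces at 458 per arm (normal approximation) or 459 (t-based), with SD 1.4, margin 0.3, one-sided 2.5% and 90% power.

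**1. Two-day tail.** Inputs: event window to last dose + 2 days (SAP 2.1.4), exposure to last dose (SAP 2.4.3.2), 24 weeks = 168 days. With a constant event rate, the overstatement for d exposure days is (d + 2)/d − 1 = 2/d.

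- d = 168: 2/168 = 1.19%
- d = 84: 2/84 = 2.38%
- d = 28: 2/28 = 7.1%

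The last two describe single early-stopping patients, not an arm. For an arm, assume a share q stops at day 84 and the rest complete:

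- q = 10%: mean exposure 0.10 × 84 + 0.90 × 168 = 159.6 days; 2/159.6 = 1.25%
- q = 5%: mean exposure 0.05 × 84 + 0.95 × 168 = 163.8 days; 2/163.8 = 1.22%
- Factor on the crude rate ratio, 10% against 5%: 1.01253/1.01221 = 1.0003

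**2. Missing last-dose date, with the events counted.** The documents give no share of affected patients. Assume a share m was treated for w weeks and the others average 23 weeks. The part of the true denominator that is lost is m·w / [(1 − m)·23 + m·w].

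- m = 1%, w = 8: 0.08/(22.77 + 0.08) = 0.35%
- m = 3%, w = 12: 0.36/(22.31 + 0.36) = 1.6%

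**3. Effect on the crude ratio if missing dates are unbalanced.** Assume 3% in one arm and 1% in the other, with the remaining patients at 168 days.

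- Affected patients treated for the full period: 0.99/0.97 = 1.021
- Affected patients treated for 84 days: [1 + 0.03 × 84/(0.97 × 168)] / [1 + 0.01 × 84/(0.99 × 168)] = 1.01546/1.00505 = 1.010

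If the shares and treatment times are equal in both arms, the factor is 1.

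**4. Illustration.** Assume a true rate of 5.00 per patient-year in 460 patients with 168 exposure days each.

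- Events over 170 days: 460 × 170 × 5/365.25 = 1,070.5
- Exposure: 460 × 168/365.25 = 211.58 patient-years; rate 5.06
- With exposure missing for 9 of the 460: 451 × 168/365.25 = 207.44 patient-years; rate 5.16

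**The case against.** **Scope.** A reader might infer that every per-patient-year hypoglycemia rate is overstated. The documents do not support that. The 12-week window is capped at Week 12, so a patient who continues past Week 12 adds no tail to the ≤12-week rate. The later-period formula in 2.5.1 counts episodes only until Week 24. (A separate matter in 2.5.1: the by-period formulas divide days by 84 or 168 instead of 365.25. Their results are 365.25/84 = 4.35 or 365.25/168 = 2.17 times smaller than true patient-year rates. That is larger than anything here and needs its own correction.)

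**Missing last-dose date.** Counting these events is an inference. The default to "classify an adverse event as treatment emergent unless there is definitive information to determine it is pretreatment or post-treatment" concerns incomplete event onset dates, not dose dates. What stands is that no rule excludes the events and that the first-dose rule makes the mismatch explicit.

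**Frequency.** One might assume that patients lost to follow-up commonly lack an end-of-treatment page. The documents give no frequency and point toward capture: Protocol 10.3 and 10.3.4 require every discontinuation to be recorded, and 9.2.1.3 requires available dosing data for the last 3 days before permanent discontinuation. Nor do they show that such patients leave because of hypoglycemia.

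**Model.** That the Poisson model excludes these patients is likewise conditional. It follows if log exposure is the offset, which the SAP does not state.

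**Reading of exposure.** Protocol 9.2.2 refers its monthly rate to days exposed within the window, which can be read as matched time. The SAP does not carry this into 2.5.1, and a programmer following 2.4.3.2 would produce the mismatch.

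**Materiality.** SAP 2.4.5 calls the safety analysis essentially descriptive, and the effects are small. This stands and limits the point to a minor correction.

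**Conclusion.** The point holds as a small correction to stated rules. The window mismatch follows directly from SAP 2.1.4 and 2.4.3.2. It raises the crude 24-week rate by about 1.2% for a completer, assuming a constant event rate through the two post-dose days, and leaves the between-arm ratio practically unchanged. The ≤12-week rate is affected only through patients who stop before Week 12.

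The missing-date mismatch is explicit for the first dose and inferred for the last. Its size, about 0.4–1.6% of the denominator, rests on assumed shares and treatment times. It reaches the crude ratio, by about 1–2%, only with an imbalance such as 3% against 1%. Whether the rate ratio would rest on different patients from the crude rate depends on the unstated offset.

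None of this touches the HbA1c analysis or the sample size.

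**What to change.** - **SAP 2.5.3, last dose.** When the end-of-treatment date is missing, take the last injection date documented on the e-CRF dosing pages, not the package return, and use it for both exposure and the on-treatment event window.
- **SAP 2.5.3, first dose.** When this date is missing, apply one rule to events and days alike, so that a patient contributes both or neither.
- **SAP 2.5.1 and 2.4.5.1.** Define time at risk for hypoglycemia as first injection to last injection + 2 days, cut at last contact and, for by-period rates, at the period boundary. State that its logarithm is the Poisson offset.

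The cost is a few SAP sentences and one derivation, with no new data: Protocol 9.2.1.3 already puts injection dates on the e-CRF. Reported rates become slightly lower. One limit remains: after Week 12 dosing is recorded mainly around visits, at dose changes and for missed injections, so the last documented injection may fall short of the true last dose.
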